### 3.5 Eligibility, Inclusion and Exclusion Criteria

#### Eligibility Criteria

Ages Eligible for Study:	18 Years to 75 Years (Adult, Older Adult)
Sexes Eligible for Study:	All
Accepts:	Persons with a clinical diagnosis of mild to moderate DSO

#### Inclusion Criteria

We are seeking otherwise healthy males or females who meet the following criteria:

- are between 18-75 years of age.
- have a clinical diagnosis of mild to moderate DSO in the nail of at least one great toe, with 20% to 50% clinical involvement of the target toenail, without dermatophytomas or lunula (matrix) involvement, without lunular or proximal involvement.
- exhibit positive mycology results (i.e., KOH test and culture of a dermatophyte) from the target great toenail, confirming common dermatophytes such as *T. rubrum*.

- are willing to refrain from using polish or other medication on treated toenails or on the skin immediately adjacent to the toenails during the treatment period unless directed to do so by the investigator.
- are willing to refrain from using topical steroids or topical antifungals on toenails or the skin immediately adjacent to the toenails or systemic antifungals for the duration of the study.
- are willing to provide signed and dated written voluntary informed consent in English before any protocol-specific procedures are performed.
- are able to complete the study and comply with study instructions.

### Exclusion Criteria

The following populations are excluded from the study:

- patients with glucose-6 phosphate dehydrogenase (G6PD) deficiency or hypersensitivity/allergies to methylene blue.
- females who are pregnant, plan to become pregnant during the study, or are nursing a child.
  - As the effect on an unborn child is unknown, all female research participants of childbearing potential must take a urine pregnancy test at screening and every 3 months (12 weeks) for the duration of the Study.
  - Hormonal methods and/or IUD must be in use at least 30 days prior to first Study intervention; barrier methods must be in use at least 14 days prior to Study intervention; vasectomy must be completed 3 months prior to first Study intervention; or in the alternative a 0 sperm count will suffice.
- persons who are hypersensitive to topical creams, ointments, medications, or surfactants.
- persons who have received systemic antifungal therapy for any reason within 3 months, or topical antifungal therapy on the toenails or skin immediately adjacent to the toenails within 3 weeks prior to the start of the study.
- persons who have received an investigational drug within 4 weeks of the first dose of study product, or who are scheduled to receive an investigational drug other than the study product during the study.
- persons who have participated in a clinical trial for the systemic treatment of onychomycosis of the toenails within 6 months prior to the first dose of study product.
- persons who are not prepared to give up use of any nail cosmetic products for the duration of the study.
- persons who have any known immunodeficiency or history of malignancy in the last 4 years, excluding nonmelanoma skin cancer.
- persons currently suffering from any disease or condition, that could include abnormal laboratory tests, and/or who are currently using medication which in the opinion of the investigator may affect the evaluation of the study product or place the subject at undue risk.

- persons with psoriasis, lichen planus, or other medical conditions known to induce nail changes, other abnormalities or can causes of nail breakdown that can predispose to secondary fungal infection. Trauma from ill-fitting shoes, running, or overly aggressive nail care can also induce changes visually indistinguishable from onychomycosis that could result in a clinically abnormal toenail.
- persons with a history of any condition that could possibly affect absorption of drug (e.g., gastrectomy), uncontrolled diabetes, clinically significant peripheral vascular disease or peripheral circulatory impairment, or has had any major illness within 30 days prior to the screening examination.
- persons with a history of drug, prescription medicine, or alcohol abuse within the past 2 years.
- smokers.

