## 1.0 Protocol Summary

Title	A Pilot Study Evaluating the Feasibility and Usability of ToeFX Light Therapy Device for Mild to Moderate Distal Subungual Onychomycosis (DSO) of the Toenail
Short Title	ToeFX light therapy pilot
Methodology	Open label, prospective, multi-site, multi-investigator
Study Sites	
Hamilton Foot Clinic [name]
 
Bruyere Foot Specialists [name]
 
Wilson Foot Clinic [name]

Number of Study Subjects	100 subjects
Diagnosis and Main Inclusion Criteria	
Healthy males or females who meet the following criteria:
 
 
• are between 18-75 years of age.
 
• have a clinical diagnosis of mild to moderate DSO in the nail of at least one great toe, with 20% to 50% clinical involvement of the target toenail, without dermatophytomas or lunula (matrix) involvement, without lunular or proximal involvement.
 
• exhibit positive mycology results (ie, KOH test and culture of a dermatophyte) from the target great toenail, confirming common dermatophytes such as T. rubrum.
 
• are willing to abstain from any other treatment for onychomycosis for the duration of the pilot study.
 

Study Product and Planned Use	The ToeFX Light Therapy system is intended as a safe, effective and non-invasive treatment for nail fungus.

	This device will be used in accordance with the attached protocol. This study will be an open-label, prospective pilot study. The subjects will be 100 patients with mild to moderate onychomycosis. The purpose of the study is to establish the efficacy of the ToeFX device, which has shown compelling results in in vitro and ex vivo (cadaver) studies but has not been tested in patients.
Primary Endpoint	Technical Success: We will monitor (a) whether subjects attain 3 mm or more of clear nail growth post-treatment (b) whether subjects show mycological cure of their infection, as verified by culturing.
Secondary Endpoints	
 
• Usability and form factor reported by clinicians
 
• Satisfaction with the treatment reported by patients
 

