### **3.3 Control**

Our study cohort will be compared to known values published in a large multicenter trial of the topical solution Jublia (manufactured by Valeant). Jublia is a once-daily treatment of 10% w/w efinaconazole for the treatment of onychomycosis. Jublia showed a complete cure rate of 15-18% in a study of two groups of 800 patients.

We will follow the inclusion and exclusion criteria defined in the Jublia trial. Patients in the Jublia study showed 20% to 50% clinical involvement of the area of the target great toenail, without dermatophytomas or lunula (matrix) involvement. Patients had positive dermatophyte culture and positive potassium hydroxide (KOH) examination from the target toenail and were not excluded for concomitant *Candida* infection. Patients were assessed for clear nail.

Based on previously published studies of photodynamic therapy for onychomycosis, we expect to observe a complete cure rate on the order of 50-80%. Given the large difference in the observed cure rate for Jublia and the anticipated cure rate for the ToeFX Light Therapy device, a sample size of 100 patients is adequate to establish statistical significance of our results.

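### The prior-treatment exclusions name only drugs, so a patient recently treated by laser, light or another device can enter, and any further clear-nail growth is credited to ToeFX

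*Combined protocol and SAP*

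**What the plan says.** The Exclusion Criteria in section 3.5 contain four look-backs on earlier treatment:

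- **Systemic antifungals, 3 months:** "persons who have received systemic antifungal therapy for any reason within 3 months".
- **Topical antifungals, 3 weeks:** "topical antifungal therapy on the toenails or skin immediately adjacent to the toenails within 3 weeks prior to the start of the study".
- **Investigational products, 4 weeks:** "persons who have received an investigational drug within 4 weeks of the first dose of study product". The same item bars anyone scheduled to receive another investigational drug during the study.
- **Earlier trials, 6 months:** "persons who have participated in a clinical trial for the systemic treatment of onychomycosis of the toenails within 6 months".

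A discretionary item covers persons with a current disease or condition, or "who are currently using medication which in the opinion of the investigator may affect the evaluation of the study product".

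Section 1.0 requires that subjects "are willing to abstain from any other treatment for onychomycosis for the duration of the pilot study". The Inclusion Criteria in section 3.5 add similar undertakings on polish, medication, topical steroids and antifungals during treatment or the study. They also require that subjects "exhibit positive mycology results (i.e., KOH test and culture of a dermatophyte) from the target great toenail", with 20% to 50% involvement of that nail.

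Section 3.4 defines success for a toenail as at least 3 mm of clear nail growth relative to baseline. It asks that the lower limit of a one-sided 95% confidence interval for the response rate be at least 50%. Section 3.3 takes the control from the published results of a topical drug trial. In section 3.2 both arms receive the photosensitizer and red light.

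**The concern.** The investigational treatment is a light device used with a painted-on photosensitizer, yet the look-backs read as if written for a drug trial. Other light-based or device-based treatment of the same nail is the earlier exposure closest in kind to the study treatment, and none of them names it.

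The protocol itself treats this class as effective. Section 3.0 says that the efficacy of photodynamic therapy has been demonstrated in the literature, and section 3.3 states: "Based on previously published studies of photodynamic therapy for onychomycosis, we expect to observe a complete cure rate on the order of 50-80" percent. Section 3.4 (Follow-up) puts complete nail regrowth at about 6 months, so outgrowth begun by an earlier treatment could continue after the baseline photograph.

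The stated purpose in section 3.0 is the efficacy of this specific device. Growth that continues from another treatment does not bear on that, and it would also blur the objective of finding how many treatments are needed. Section 4.1 recruits patients who present to clinicians with onychomycosis, so earlier treatment is plausible, although the documents do not say how often it occurs.

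**Working it through.** **Step 1. Does any provision reach earlier device treatment?**

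| Provision | Location | Reaches earlier laser, light or other device treatment? |
|---|---|---|
| Systemic antifungal, 3 months | 3.5 Exclusion | No, drugs only |
| Topical antifungal, 3 weeks | 3.5 Exclusion | Not laser or light alone; photodynamic treatment with a painted-on agent only by a stretched reading |
| Investigational drug, 4 weeks | 3.5 Exclusion | Not a device; an unapproved photosensitizer arguably |
| Trial of systemic treatment, 6 months | 3.5 Exclusion | No |
| Investigator opinion | 3.5 Exclusion | No; limited to current disease, condition or medication, and a completed procedure is none of these |
| Abstention and refrain rules | 1.0, 3.5 Inclusion | No; they look forward from entry |
| Adoption of the comparator trial's criteria | 3.3 | Not shown; the criteria quoted there say nothing about devices |

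The gap is clear for laser or light alone. For photodynamic treatment it is at least arguable within 3 to 4 weeks, and clear beyond that.

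**Step 2. What limits the harm?**

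- Baseline clear nail is subtracted (3.4), so only growth of 3 mm or more after baseline can be miscredited.
- Positive KOH, positive culture and 20-50% involvement are required (3.5), so a nail that has already cleared does not qualify.
- Mycology is part (b) of the primary endpoint (1.0) and is assessed among clear-nail responders (3.4). A negative result does not show which treatment produced it.
- Both arms are active and the control is external (3.2, 3.3), so nothing within the trial would expose carry-over.

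**Step 3. Illustration of size.** The documents give no figure for this bias, so there is none to reproduce.

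Inputs from the documents: N = 100 (1.0, 3.3) and a one-sided 95% lower limit of at least 50% (3.4). Assumptions: the criterion is applied to all 100 subjects together; true ToeFX response is 50%; a fraction f of subjects had recent device treatment and responds at rate q.

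*Threshold.* The exact (Clopper-Pearson) lower limit for r responders is the 5th percentile of Beta(r, 101 − r). It is 49.3% at r = 58 and 50.3% at r = 59, so 59 responders are needed. Wilson and Wald limits give the same threshold.

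*Chance of meeting it.* With k = 100f, responders = Binomial(100 − k, 0.50) + Binomial(k, q), and the chance is P(responders ≥ 59). The expected rate is (1 − f) × 0.50 + f × q.

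| f | q | Expected rate | P(≥ 59) |
|---|---|---|---|
| 0 | – | 50.0% | 4.4% |
| 1% | 80% | 50.3% | 5.0% |
| 2% | 80% | 50.6% | 5.6% |
| 5% | 80% | 51.5% | 7.9% |
| 10% | 80% | 53.0% | 13.1% |
| 15% | 80% | 54.5% | 20.6% |
| 10% | 60% | 51.0% | 6.6% |
| 10% | 100% | 55.0% | 23.0% |
| 10% | 40% | 49.0% | 2.8% |
| 10% | 30% | 48.0% | 1.7% |

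For example, at f = 10% and q = 80%: 0.90 × 0.50 + 0.10 × 0.80 = 0.53. At q = 40%: 0.90 × 0.50 + 0.10 × 0.40 = 0.49.

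**The case against.** The strongest reply is that the entry criteria and the endpoint already do most of the work. A recently treated patient who still has positive KOH and culture is one in whom the earlier treatment did not eliminate the fungus. Such patients may be harder to treat, and including them could lower the observed rate. The 80% in the illustration is borrowed from the top of the range in section 3.3, which is for complete cure, not for 3 mm of growth among patients still culture-positive. Nothing in the documents says how common device treatment is at these clinics, and at 1-2% the effect is small. All of this stands, and it is why neither the size nor the direction of the bias can be claimed.

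It does not remove the gap. A nail with live fungus left distally passes the entry criteria, and any growth that continues after baseline is scored as response.

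Two stronger readings are tempting, and neither is supported:

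- A reader might infer that clear nail produced by an earlier treatment is counted as a ToeFX success. It is not: section 3.4 measures change from baseline.
- A reader might infer that the protocol washes out only weak treatments and leaves the strong ones in. Topical therapy (6-23% cure, section 2.0) is washed out, but so is oral therapy, which section 2.0 puts at 45-70% cure, overlapping the 50-80% in section 3.3.

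**Conclusion.** The concern holds as a gap in eligibility. As written, the criteria admit a patient recently treated by laser, light or another device, provided that mycology is still positive and involvement is 20-50%. Any further growth in that patient is credited to ToeFX, with no concurrent untreated group to show carry-over. This follows from the text and does not depend on the illustration.

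The effect on the result is unknown in size and direction. Under the assumptions above, the chance of meeting the clear-nail criterion at a true 50% response moves from 4.4% to 5.0-20.6% if 1-15% of subjects carry over at 80%, and to 2.8% if 10% respond at 40%. The share of such subjects and their response rate are assumptions without support in the documents. A reader should not take the table as evidence that the trial is biased towards success. The change is still worth making, because it affects who is enrolled and costs almost nothing.

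**What to change.** In the Exclusion Criteria of section 3.5:

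1. Replace *investigational drug* with *investigational drug or device* in the 4-week item, for both prior and scheduled use.
2. Add an exclusion for laser, light, photodynamic or other device-based treatment of the target toenail within a stated period before the first study treatment. The sponsor should set that period and justify it against the regrowth time of about 6 months in section 3.4. That figure is given there for follow-up, so it does not by itself fix the length of a washout.
3. Record all prior treatment of the target nail, with dates, at screening.

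The cost is two wording changes and one history question. A few candidates would be excluded or deferred. The sample size does not change.

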### **3.6 Data Analysis**

- Descriptive statistical analysis to analyze degree of response (e.g., complete response or clearing, >75% clear, 50-75% clear).
- Increase in clear nail at each timepoint of evaluation after the last treatment
- Increase in clear nail as a function of the number of treatments

To evaluate the overall response rates, we plan to ensure that the study report be presented in a tiered fashion, citing the success rate for the subjects exhibiting mycological cure concurrent with clear nail, with separate presentation of the data for subjects exhibiting mycological cure with residual nail dystrophy.

## **4.0 Study Procedures**

### **4.1 Patient Recruitment and Screening**

Potential study subjects will be identified by the co-investigators or any sub-investigators. It is anticipated that surgical consults will be the primary source of study candidates. Clinicians will ask patients who present with onychomycosis if they are interested in participating in the research trial; those who are interested will be assessed by the clinician for their compatibility with the inclusion/exclusion criteria. Patients that meet all criteria will be asked to submit a nail sample for mycological culturing. This initial review of existing patient information may be performed prior to subject consent; however, no protocol-driven tests or procedures may be performed until after informed consent has been obtained. If the subject shows positive mycology, he/she will be contacted via phone within 2 weeks and asked to sign an informed consent form in person, where a clinician will be present to answer any questions. If the patient is satisfied and has no questions, the treatments may commence at the clinic during the same visit. Research participants will remain in the study for one year.

For the occasional non-English speaking study participant, an on-site translator will be provided at the clinic at the expense of the Sponsor. Informed consent will be treated as an ongoing

process throughout a study. For those who understand English but cannot read, talk, or write, the investigator will provide the necessary support to ensure the subject's ongoing comprehension of new information that may become available during the study.

## **4.2 Informed Consent**

Consent shall be obtained in accordance with Canada's Medical Device Regulations section 81(k)(ii) and the Tri-Council Policy Statement – Ethical Conduct for Research Involving Humans (TCPS2) and World Medical Association Declaration of Helsinki – Ethical Principles for Medical Research Involving Human Participants. Potential subjects must be informed as to the purpose of the study and the potential risks and benefits known or that can be reasonably predicted or expected as described in the written consent form. The patient shall have sufficient opportunity to consider participation in the study; consent forms shall be written in English. A patient cannot be led to believe that they are waiving their rights as a subject or the liability of the sponsor or investigator. Patients are then invited to sign and date the consent form, indicating their consent for enrollment (investigators may not date the consent form on the patient's behalf.) Once a patient has signed and dated the consent form, they are considered a subject enrolled in the study.

The person administering the consent signs and dates the consent form to indicate that the purpose, risk and benefits of the study were explained to the subject/caregiver and their signatures witnessed. Only study personnel who have been delegated by the Principal Investigator or Co-Investigators to perform this task may obtain informed consent and sign the consent forms.

The investigators will retain the original copy of the consent forms, signed and dated by the subject/caregiver, in the Investigator's Study File. A duplicate copy shall be provided to the subject.

## **4.3 Identification and Enrollment Log**

Subjects who have signed the consent form will be given a unique subject number that shall be used to identify the subject on all study related documents. The Enrollment Log relates the subject number to the full name, address, telephone number and any other pertinent subject information. Once assigned a subject number, the investigator shall enter the remaining subject identification information into the log. This log is the primary way in which the subject identification is correlated to the actual identity of the subject. The Enrollment Log will be kept in a secure location with restricted access to only study staff, ensuring confidentiality is strictly maintained.

## **4.4 Subject Withdrawal**

Subjects may be withdrawn from the study for any of the following reasons:

1. Subject's choice to withdraw their consent to participate. Any participant has the right to withdraw from the study at any time and for any reasons without prejudice to future medical care by the physician or the institution.
2. Investigator's choice to withdraw the subject from the study. An investigator may choose to withdraw a subject from the study due to changes to their medical condition which could interfere with their participation or if the study may interfere with their prompt and effective treatment.
3. Study termination for either administrative or safety reasons.

For participants who withdraw their consent for study participation, the Investigator will complete the "Subject Withdrawal" and no additional data will be collected after the date of their discontinuation.

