### **3.4 Outcome Measures**

Clear nail: The specifications for clear nail are described below. The 95% one-sided confidence interval (i.e., lower bound only) around the observed response rate as described below should be  $\geq 50\%$ .

We will monitor whether subjects attain 3 mm or more of clear nail growth post-treatment. We will verify by taking a photograph prior to every treatment to assess the change in millimeters (mm) of clear nail bed. Millimeters (mm) of clear nail from the base of the toenail will be determined from digital photographs of the toenail and verified via software. The change in mm of clear nail bed will be calculated as the difference in mm of clear nail bed from baseline measurement to the measurement at the end of the procedure administration phase.

An increase in mm of clear nail between the two measurement points indicates that the toenail has improved and is positive for study success. A decrease in mm of clear nail between the two measurement points indicates that the toenail has worsened and is negative for study success.

Individual toenail success criterion is defined as 3 millimeter (mm) or more of clear nail growth as evaluated relative to baseline.

Length of the unaffected part of the target nail is measured in millimeters along the midpoint from the nail fold to the proximal border of the affected part (lowest point affected) along the midpoint of the target nail. Change from Baseline is: (Baseline value subtracted from 6-month treatment value). P-value shall be based on analysis of variance (ANOVA) with treatment and pooled center. Statistics will be provided for the adjusted least square mean.

To ensure adequate photographic quality and to maximize our ability to compare photographs across timepoints and across subjects, a standardized photography protocol will be put in place. Photographs shall be of high quality and high resolution. An internal scale (e.g. ruler) will be included in all images to allow objective measurement of millimeters of clear nail regardless of magnification of the image.

**Mycology:** Among toenails which are deemed responders based on the “clear nail” criteria, we will also assess for negative mycology (negative stain with concurrent negative culture, or two negative cultures from the same nail).

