**Follow-up:** The goal of treatments for onychomycosis is elimination of the fungal organism and full clearance of the nail. Follow-up for this indication should be based on the anticipated time for complete nail regrowth, which is approximately 6 months. Longer follow-up times will be helpful for assessing recurrence rates. To control for loss of subjects who do not exhibit the desired visual outcome, subjects who drop out or are lost to follow-up will be considered as treatment failures for this indication.

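### The single-timepoint ANOVA of mm change makes no provision for subjects without a 6-month value, so mean clear-nail growth would be overstated if poor responders leave more often

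*Combined protocol and SAP*

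**What the plan says.** Section 3.4 (Outcome Measures) defines the continuous outcome: "Change from Baseline is: (Baseline value subtracted from 6-month treatment value". For the analysis, "P-value shall be based on analysis of variance (ANOVA) with treatment and pooled center", and "Statistics will be provided for the adjusted least square mean". Earlier in the same section, the change is instead taken from baseline "to the measurement at the end of the procedure administration phase". Images are to be collected by "taking a photograph prior to every treatment".

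The Follow-up paragraph of Section 3.4 gives the only rule on incomplete follow-up. It opens with its purpose, "To control for loss of subjects who do not exhibit the desired visual outcome", and then states that "subjects who drop out or are lost to follow-up will be considered as treatment failures for this indication". Section 4.4 adds, for participants who withdraw consent, that "no additional data will be collected after the date of their discontinuation".

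Neither Section 3.4 nor Section 3.6 (Data Analysis) names an analysis set, an imputation rule or a sensitivity analysis for a missing 6-month mm value.

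**The concern.** The plan recognises that loss may be related to outcome and protects one result from it. Counting drop-outs as failures gives every subject a status for the responder rate. It does not say how many millimetres a drop-out grew, so it does not reach the ANOVA. An analysis of 6-month minus baseline at one timepoint loses any subject without the 6-month measurement, even when several earlier images exist for that subject.

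Two results are exposed. The first is the least-squares mean of growth, which would describe those who stayed. The second is the comparison of red light with red plus blue light, which Section 3.2 gives as an aim; it would be distorted if the arms lose poor responders at different rates.

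**Working it through.** **Inputs from the documents.** 100 subjects; success at 3 mm or more of growth; 12 treatments over 1 year (Sections 2.1 and 3.2); two-week intervals (Section 2.2). The plan gives no SD, expected mean, drop-out rate or power for the mm outcome, so it has no figure of its own to reproduce here.

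**Assumed inputs.** True mean growth 3 mm, SD 2 mm, drop-out 10 to 30%, and the mechanisms described below.

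**Step 1: simple bound.** Let d be the share lost and D the completers' mean minus the drop-outs' mean. The completers' mean exceeds the all-subject mean by d × D.
- 10% lost, 1 mm worse: 0.10 × 1 = 0.1 mm.
- 30% lost, 2 mm worse: 0.30 × 2 = 0.6 mm.
- Drop-out unrelated to growth: D = 0, so the shift is 0.

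**Step 2: a selection model.** Let rho be the correlation between growth and the tendency to stay. The shift is rho × SD × φ(z_d) / (1 − d), where z_d is the normal quantile at d. With SD 2 mm and rho 0.5:
- d = 10%: 0.5 × 2 × 0.1755 / 0.90 = 0.19 mm.
- d = 20%: 0.5 × 2 × 0.2800 / 0.80 = 0.35 mm.
- d = 30%: 0.5 × 2 × 0.3477 / 0.70 = 0.50 mm.

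At rho = 0 every shift is zero. At rho = 1, where exactly the worst growers leave, the shifts double; that is a limiting case, not an expectation.

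**Step 3: simulation by visit.** Growth is linear, reaching a subject-specific value at the endpoint (mean 3, SD 2 mm), with measurement error SD 0.5 mm. From the fifth visit, the chance of leaving at each visit is 12% if the last measured change was below 0.5 mm, and 1% otherwise.

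| Setting | Drop-out | All subjects | Completers | Shift |
|---|---|---|---|---|
| 12 visits before the endpoint | 19% | 3.00 mm | 3.34 mm | +0.34 mm |
| Endpoint at visit 6, same chances | 5% | 3.00 mm | 3.09 mm | +0.09 mm |
| Equal 3% chance at each visit | 6 to 22% | 3.00 mm | 3.00 mm | about 0 |

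The first two rows correspond to the two schedules in the documents. At two-week intervals all 12 treatments fit within 6 months. Spread evenly over a year, 6 months falls near visit 12 × 26/52 = 6.

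In the first setting a random-slope mixed model on all images returned 2.99 mm. Giving drop-outs zero change returned about 2.7 mm, which is too low.

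**Step 4: the arm comparison.** With equal loss and the same mechanism in both arms, the shifts cancel. With 10% loss in one arm and 30% in the other, SD 2 mm, the net shift is 0.50 − 0.19 = about 0.3 mm at rho 0.5, and about 0.6 mm at rho 1. It favours whichever arm loses more subjects.

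**Step 5: the responder rule.** Drop-outs are failures, so all subjects stay in the denominator. The test that the one-sided 95% lower bound is at least 50% is not touched.

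**The case against.** The strongest reply is that the plan is silent rather than wrong. A reader might infer that it restricts the ANOVA to completers. No section says so; that restriction is a consequence of the outcome definition and the single-timepoint method. This stands as a matter of wording, but the consequence follows all the same.

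A reader might also take Section 3.4 to say that those who leave are the poor responders, and conclude that the mean is biased upward. The paragraph guards against that possibility; it does not report who leaves. The bias is therefore conditional, and zero is within its range.

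Section 4.4 is weak support by itself. It covers consent withdrawals only, not loss to follow-up or withdrawal by the investigator, and a subject who withdraws after month 6 of a one-year study still has the value. Stopping data collection then is ordinary consent practice.

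Nor are the interim images wasted altogether: Section 3.6 plans to describe growth by number of treatments. They simply do not enter the ANOVA.

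The good performance of the mixed model in the simulation is partly built in, because leaving depended only on observed growth. Finally, an unstructured covariance over 12 visits would need 12 × 13 / 2 = 78 parameters from 100 subjects, which is not a sensible first choice. Both points shape the remedy below.

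**Conclusion.** The point holds in conditional form. As written, the mm-change analysis can use only subjects with a 6-month value, and the failure rule does not fill the gap. If poor responders leave more often, which the plan itself treats as a risk, the least-squares means of growth would be too high.

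The size cannot be derived from the documents. Under the stated assumptions it runs from zero (drop-out unrelated to growth), through about +0.1 mm (6 months near visit 6) and about +0.35 mm (12 visits before the endpoint), to about +0.6 mm (30% loss of subjects 2 mm worse).

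It would be tempting to extend the upward bias to the ANOVA p-value. That is not supported: the treatment term tests the difference between arms, whose bias needs differential loss and has no fixed direction. The responder criterion is unaffected. This should be corrected before analysis, but it does not undermine the success test.

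**What to change.** In Section 3.4, replace the single-timepoint ANOVA with a mixed model for repeated measures on mm change, using the photographs already planned before each treatment. Terms: arm, visit, arm-by-visit, site and baseline mm. Include every subject with at least one post-baseline image, and report the 6-month means and the arm contrast. Use a small set of prespecified visits, a structured covariance or random slopes rather than an unstructured covariance over all visits.

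Add a sensitivity analysis giving drop-outs zero change, labelled as conservative rather than unbiased. It is needed because the mixed model is valid only if drop-out depends on growth already observed.

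Reconcile the end measurement, which Section 3.4 gives both as 6 months and as the end of the procedure phase. Sections 2.1, 2.2 and 3.2 must be brought into line on visit timing, so that the image supplying the endpoint is identifiable.

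The cost is revised wording and a little more programming, with no new visits or subjects, plus reliance on a missing-at-random assumption. Random slopes, if chosen, also assume linear growth.
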